HVLT Total	(6.20)	(6.75)	28.81 (6.52)	26.02 (5.42)	(4.19)	27.96 (5.44)
	9.03	9.48			9.93	
HVLT Delayed	(2.70)	(1.86)	9.73 (2.22)	8.93 (2.26)	(2.08)	9.60 (2.74)
WMS Immediate	17.19	22.28			24.00	
Recall	(9.53)	(8.15)	23.35 (7.81)	18.27 (7.90)	(6.49)	24.72 (5.62)
WMS Delayed	5.22	6.72			7.27	
Recall	(2.88)	(1.85)	7.58 (4.30)	6.27 (2.39)	(1.17)	7.36 (1.47)
	16.01	18.90			21.22	
Rey-O 3-min	(5.93)	(6.85)	18.77 (8.48)	16.80 (5.29)	(6.76)	22.63 (7.19)
-	16.71	19.10	. ,		20.88	. ,
Rey-O 30-min	(6.36)	(7.65)	20.31 (7.11)	16.69 (5.34)	(7.38)	23.60 (6.92)

[figure not shown]
 Table 2. Pilot Data: Cognitive Outcome Measures in the Kundalini Yoga and Memory

 Enhancement Training Groups

[figure not shown]

Executive Functioning

fMRI in meditators showed higher activity in a functional network including the anterior cingulate, fronto-orbital cortex and insula

We also explored the relationship between performance on memory tests and resting-state functional connectivity before and after KY vs. MET. Resting-state (rs-) fMRI was used to map correlations between brain networks and memory performance changes over time. Default mode networks (DMN), language and superior parietal networks were chosen as networks of interest to analyze the association with changes in verbal and visuospatial memory performance. Fourteen KY and 11 MET participants completed the rs-fMRI portion of the study. We observed improved verbal memory performance correlated with increased connectivity between the DMN and frontal medial cortex, pregenual anterior cingulate cortex, right middle frontal cortex, posterior cingulate cortex, and left lateral occipital cortex (see figure on right). Improved verbal memory performance positively correlated with increased connectivity between the language processing network and the left inferior frontal gyrus. Improved visuospatial memory performance correlated inversely with connectivity between the superior

parietal network and the medial parietal cortex. Thus KY may be as effective as MET in improving functional connectivity in relation to verbal memory performance.

Study Design:

a) Rationale for duration of interventions and follow up:

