outcome will be an average of the participant's z-scores on three tests. Two of these tests will be of verbal memory tests: 1) the Hopkins Verbal Learning Test (HVLT) (total and delayed recall scores) (Shapiro et al., 1999), and (2) the Wechsler Memory Scale (WMS-IV) (immediate and delayed) and one will be of visual memory (the Rey-Osterreith Complex Figure 3-minute delay recall). The secondary outcome measure of executive functioning will include Trail Making B and Stroop Color-Word Interference tests to estimate mental flexibility and inhibition/adjustment of behavior. Tests of language fluency will include Animal fluency and CFL Letter Fluency to assess strategic searching/organization of verbal knowledge, as well as the Boston Naming Test. The battery will also include measures of attention/ processing speed which are commonly impaired in the geriatric population according to prior research by our group (Schneider, [name], Siddarth, & [name], 2012) and others (Alexopoulos, Kiosses, Klimstra, Kalavam, & Bruce, 2002; Bhalla et al., 2009; Butters, 2004; Favrod et al., 2015; Lockwood, Alexopoulos, & van Gorp, 2002). These tests place significant demand on mental operations that require speed, manipulation and monitoring of information that is in conscious awareness (Trail Making A; Digit Span; Stroop Color and Word). Most of the measures have 2 or 4 alternate forms so that unique forms may be administered to participants during repeat testing. We include both traditional, standardized tests and computerized tests for enhanced sensitivity of the battery to potential intervention effects and so that our results can also be compared with other findings in the literature. In addition to the cognitive outcome measures, we will include the TOPF to estimate pre-morbid cognitive functioning.

Secondary clinical outcome measures will include the Clinical Global Impression- Severity and Improvement scale (CGI)(Busner, Targum, & Miller, 2009) to quantify overall severity and clinical improvement over time (2 min). Subjective memory complaints will be assessed via the 10-item Memory Functioning Questionnaire scale. The Beck Depression Inventory (BDI) (Beck, Steer, & Brown, 1996; Beck, Steer, & Carbin, 1988), a self-assessment scale of depression (5 min), will also be administered, as will the Hamilton Anxiety scale.

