In the fitting method, f(i) is CBF at each individual delay and the final CBF is the mean of the estimated CBF per PLD. The 5 PLDs allow us to estimate CBF and ATT simultaneously using parameters fitting (2). Resulting rCBF and ATT maps will then be co-registered with the T1-weighted structural scan and normalized to the MNI standard space template with subsequent spatial smoothing.

WM Hyperintensities (WMH). The 3D T2-space images will be used to visualize WMHs by employing a semiautomated WMH identifier (Schwarz, Fletcher, DeCarli, & Carmichael). Briefly, WMH burden will be assessed based on the signal intensities of co-registered 3D MEMPR and T2-SPACE images, and population statistics on the spatial distribution and neighborhood structure of WM lesions. With every unit increase in WM burden, we will estimate % reduction in local brain tissue volume. GLM and multiple regression analyses will determine links between WM burden, clinical measures and vascular risk factors in each treatment group that may need to be controlled for.

Integration with Mood and Neurocognitive Measures. To test hypotheses about the relationships between imaging metrics and change in mood and cognition, we will derive domain summary scores for the 3 domains of interest – i.e., mood, memory, and executive functioning. Percent change in the mean Z scores will be calculated for each domain score and entered into analysis. We will first test the specific hypotheses described in the aims using separate GLMs for each MRI method. *Integration of Predictive Variables.* After analysis is complete on the predictive validity of each MRI measure, those that significantly predict remission/relapse or cognitive decline at follow-up will be combined for regression analysis. We will use the best single predictor in each modality. The final analysis will include a step-wise multiple regression analysis of clinical outcomes.

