Data will be analyzed using the SAS (v9.4) statistical package. Data will be examined initially to identify issues such as departures from normality, which might suggest the need for transformation (e.g., logarithmic). Demographic variables (e.g., age, gender, etc.) will be compared by treatment group and examined in relation to outcome variables; this would define one possible set of appropriate covariates, if needed. Correlations (a) among outcome measures and (b) among potential covariates will be examined to eliminate redundancy via possible data reduction, e.g., formation of composite scores or selection of single measures from sets of highly inter-correlated variables. Cognitive domain scores will be obtained as follows: for each neuropsychological test, raw scores will be converted to standardized (Z) scores with a mean of 0 and a SD of 1, based on all participants combined. Then, for each of the tests in a cognitive domain, the Z scores will be averaged to create a single Z score per cognitive domain.

The independent samples *t*-test or Chi-square test will be used to compare the demographic characteristics between the MET and KK+KY control group. The effect of intervention over time on the cognitive functions will be investigated in intention-to-treat (ITT) analyses. Measurements will be analyzed using linear mixed models; analyses will assume missing at random with missingness allowed. All models will include random intercepts to account for correlations between the repeated measures for each participant. The fixed components of the models will include effects of group and time and a group X time interaction, with post hoc analyses between times and groups. All statistical significance tests will be two-sided, and an alpha-level of 0.05 will be considered statistically significant for primary analyses and Bonferroni correction will be employed for post hoc analyses.

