Primary outcome: The analyses for the memory domain Z scores will use general linear mixed model (GLMM) analysis (e.g., SAS PROC MIXED). The two treatment groups will be compared for time course of cognitive domain z scores the initial endpoint EOT at 12 weeks and 6- and 12-months. Covariates may be included in the model as noted above. As noted above, the primary cognitive domain of interest for this proposal is memory. A separate GLMM as above will be estimated using memory domain z-scores as dependent variables. Executive Function will be examined as secondary outcome measure. Supplementary analyses of the follow-up period will look at the cognitive domain scores by treatment group controlling for values at EOT (post-treatment changes). Objective memory measures will be examined using a similar GLMM.

Exploratory Hypotheses: GLMM models as described above will be used to examine telomerase activity (overall level and TL) and inflammatory measures separately. Relationships between changes in markers of inflammation and telomerase activity to changes in cognitive scores, cognitive domain scores and fMRI measures will be examined using regression models within each group. Transformations of the measures will be performed as necessary.

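### Imaging–cognition analyses use percent change in Z scores centred on zero, which removes almost all sensitivity to real cognitive change

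*Combined protocol and SAP*

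**What the plan says.** In the combined protocol and SAP, the section Integration with Mood and Neurocognitive Measures plans this for the links between imaging and clinical change: "we will derive domain summary scores for the 3 domains of interest – i.e., mood, memory, and executive functioning". The next step is "Percent change in the mean Z scores will be calculated for each domain score and entered into analysis". The analysis follows: "We will first test the specific hypotheses described in the aims using separate GLMs for each MRI method". MRI measures that predict significantly then go forward to a combined regression.

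The scale of the cognitive scores is set under Data analysis: "raw scores will be converted to standardized (Z) scores with a mean of 0 and a SD of 1, based on all participants combined". Then "the Z scores will be averaged to create a single Z score per cognitive domain". The memory composite is described under the neuropsychological tests: "outcome will be an average of the participant's z-scores on three tests".

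The plan gives no percent-change formula, offset, absolute-value divisor or rule for baselines near zero. It also does not say whether the standardisation uses baseline data or all visits. Under Exploratory Hypotheses, the same domain scores enter other regressions without any mention of percent: "Relationships between changes in markers of inflammation and telomerase activity to changes in cognitive scores, cognitive domain scores and fMRI measures".

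**The concern.** Percent change needs a scale with a true zero and a positive baseline. A sample-standardised Z score has neither: its zero is the average of the women enrolled. Dividing by it has two effects. The sign of the result depends on which side of the sample average a woman started, and its size depends mainly on how close to that average she was. Neither reflects how much she changed.

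At stake is the plan's stated method for linking imaging metrics to memory and executive change. A null result from this metric would carry almost no information but could be read as evidence of no brain–cognition link. Because only significant MRI measures go forward, missed associations would also affect the later combined model.

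**Working it through.** **Inputs from the documents.** Planned completers: 90 (Power analysis). Tests are two-sided at 0.05 (Data analysis). The memory composite averages three tests. The imaging sample size is not stated. I use 90, an intermediate 50, and 25, the pilot's resting-state total ("Fourteen KY and 11 MET participants completed the rs-fMRI portion of the study").

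Pilot gains at 12 weeks in baseline SDs (Table 2):
- KY: HVLT delayed (9.48 − 9.03)/2.70 = 0.17; WMS delayed (6.72 − 5.22)/2.88 = 0.52; Rey-O 3-min (18.90 − 16.01)/5.93 = 0.49. Mean 0.39.
- MET: (9.93 − 8.93)/2.26 = 0.44; (7.27 − 6.27)/2.39 = 0.42; (21.22 − 16.80)/5.29 = 0.84. Mean 0.57.

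**Assumptions not in the documents.** Normal scores. Composite SD 0.73–0.86, which is √((1 + 2c)/3) for an inter-test correlation c of 0.3 to 0.6. Retest correlation 0.6–0.8. True correlation between the MRI predictor and Z change 0.4. Mean gain 0.2–0.57.

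**The plan's own figures.** None is given for this analysis. The two figures in the Power analysis section do reproduce: an effect of 0.60 with 45 per group gives 80.4% power (t test), and the 0.62 equivalence margin gives 79.9% (two one-sided tests at 0.05).

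**Step 1: the ratio.** Percent change = 100 × (F − B)/B, with B baseline and F follow-up. The same gain of +0.4 gives:

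| Baseline Z | Follow-up Z | Percent change |
|---|---|---|
| −0.5 | −0.1 | −80% |
| −0.05 | 0.35 | −800% |
| 0.05 | 0.45 | +800% |
| 0.5 | 0.9 | +80% |
| 1.0 | 1.4 | +40% |

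**Step 2: how often the sign is wrong.** The sign is reversed whenever B < 0. If Z is scaled to baseline, that is 50% of women. If Z is scaled over all visits, the baseline mean sits at minus half the gain, so the share is Φ(gain/(2 × SD)). The extremes are Φ(0.2/1.72) = Φ(0.12) = 0.55 and Φ(0.57/1.46) = Φ(0.39) = 0.65. Simulation agrees. Percent change exceeds 500% in absolute value for 8–15% of women.

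**Step 3: power with simple change, by formula.** Power ≈ Φ(√(n − 3) × atanh(0.4) − 1.96), with atanh(0.4) = 0.4236.
- n = 90: Φ(9.327 × 0.4236 − 1.96) = Φ(1.99) = 0.977
- n = 50: Φ(6.856 × 0.4236 − 1.96) = Φ(0.94) = 0.828
- n = 25: Φ(4.690 × 0.4236 − 1.96) = Φ(0.03) = 0.511

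**Step 4: power by simulation** (4,000 trials per setting, range over the settings above):

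| Outcome entered | n = 90 | n = 50 | n = 25 |
|---|---|---|---|
| Simple change in Z | 97–98% | 83–85% | 51–55% |
| Follow-up Z adjusted for baseline Z | 94–97% | 73–81% | 41–48% |
| Percent change, signed baseline | 5–7% | 5–7% | 5–7% |
| Percent change, absolute baseline | 14–31% | 13–24% | 10–18% |

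With no true association, signed percent change rejects 4.4–5.4% of the time.

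**Step 5: other correlations.** A separate simulation with 90 women gave, at a true correlation of 0.3, 83–85% (simple change), about 6% (signed) and 14–15% (absolute baseline). At 0.5 it gave about 100%, 6–7% and 28–32%.

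**The case against.** The strongest reply is that the plan gives no formula, so 5–7% describes only one reading. Dividing by the absolute baseline restores the sign. The Data analysis section also provides for checking normality and transforming where needed. This has some force: in one setting (SD 0.8, retest 0.7, gain 0.43, 90 women), ranking the absolute-baseline version gave 82–87% power, though less is recovered when gains are larger. But it needs two steps that the plan does not state for this analysis. The only transformation the plan gives as an example, a logarithm, cannot be applied to negative values. Ranking the signed version leaves power between about 6% and a quarter, because ranks do not repair a reversed sign.

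Other points stand and limit the finding:
- The imaging aims are labelled exploratory, and no numbered hypothesis tests imaging against memory change.
- With 25 women, even simple change has only 51–55% power at a correlation of 0.4.
- The word changes under Exploratory Hypotheses is not defined as a simple difference. The apparent use of two metrics for one score is therefore an ambiguity, not a proven contradiction.
- Z scores are defined only for the neuropsychological tests, so the problem is an inference for mood.
- Simple change can pick up regression to the mean. Suppose an MRI metric correlates 0.4 with baseline memory and has no link to follow-up beyond that. With a retest correlation of 0.7, its correlation with change is −0.4 × 0.3/√0.6 = −0.155, and simple change rejects about 30% of the time at n = 90. The baseline-adjusted model stays near 5%.

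**Conclusion.** The metric is wrong as written for the memory and executive scores and should be corrected. The sign reversal and the instability near zero follow from the plan's own definitions. The power figures depend on the assumed correlations, but the collapse under a signed divisor appeared in every setting tried. With the absolute baseline and no transformation, power at 90 women and a correlation of 0.4 is still at most 31%, against 97–98% with simple change.

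The consequence is lost sensitivity in the exploratory imaging–cognition models, not extra false positives. The primary memory and secondary executive mixed models use the Z scores directly, and the group comparisons of imaging change do not use percent change.

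**What to change.** In Integration with Mood and Neurocognitive Measures, replace percent change with one of two outcomes: follow-up Z modelled on the MRI metric with baseline Z as covariate, or follow-up Z minus baseline Z. The adjusted model is safer when the MRI metric may be related to baseline cognition.

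State four further items before analysis:
- Every visit is standardised with the pooled baseline mean and SD of each test.
- All tests point the same way before averaging, for example by reversing Trails B if it is scored as time. This and the previous item also affect the domain scores in the main mixed models, so they belong in the Data analysis section.
- The cognitive follow-up visit is named. MRI is at baseline and 12 weeks. The general statement on outcome measures includes week 12, but the neuropsychological paragraph and Table 4 omit it for the battery.
- The mood domain score is defined and treated in the same way, and the changes under Exploratory Hypotheses are defined to match.

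A separate small repair in the same paragraph: replace the undefined remission/relapse outcome with change in the plan's own domain scores, keep cognitive decline at follow-up, and label the best-predictor and stepwise model exploratory.

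The cost is a wording change. The change metric itself needs no new data or visits.

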We designed the present randomized trial to test whether 12 weeks of supervised weekly Kundalini yoga class and a brief daily home meditation practice can improve cognitive function among older women with high AD risk compared to weekly classes of memory training with daily homework. Our choice of interventions is based on prior studies of mind-body exercise in older adults that revealed robust cognitive benefit, as well as our own studies of this intervention compared to cognitive memory training in older adults with MCI. Kundalini yoga has also been observed to impact the frontal lobes, likely due to increased cerebral blood flow ([name] et al., 2013b).

The primary outcome will be memory performance at 12 weeks (i.e., immediately post-treatment).

Secondary outcomes include measures of executive functioning and changes in brain structure and connectivity.

Specific Aim 1: To evaluate effects of Kundalini Yoga+ Kirtan Kriya (KK+KY) and Memory Enhancement Training (MET) on memory performance in women with high AD risk.

Hypothesis 1: Improved memory performance will be observed in women receiving KK+KY and MET at 12 weeks compared to baseline.

Specific Aim 2: To test the efficacy of KK+KY vs. MET for improving executive functioning including working memory.

Hypothesis 2: KK+KY will improve performance in executive functioning to a greater extent than MET.

Exploratory Aim 3a: To test the effects of MET vs. KK+KY on structural and functional connectivity and task-related activation for working and episodic memory.

Hypothesis 3a: Compared to MET, KK+KY will be associated with greater improvement in connectivity in regions associated with working and episodic memory.

Exploratory Aim 3b: To test the effects of MET vs. KK+KY on levels of cellular and genomic markers of inflammation, telomerase activity level, and telomere length after 12 weeks and at 6 and 12 month follow-up.

Hypothesis 3b: Compared to MET, KK+KY will be associated with decreases in cellular and genomic markers of inflammation and increases in telomerase activity level and telomere length after 12 weeks and at 6 and 12 month follow-up.

Exploratory Aim 3c: To explore whether KK+KY results in reduced cardiovascular risk factors compared to MET, and whether this effect will correlate temporally with changes in fMRI measures and clinical outcomes.

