Screening Procedures: Potential participants will receive a telephone screening. Only participants who are naïve to Kundalini Yoga and Kirtan Kriya or who have not practiced in the past year will be included in the study. Only participants currently not taking psychotropic medications prior to the initiation of the study will be enrolled. A research coordinator will assist with recruitment, screening, and scheduling.

A member of the research team will obtain informed consent from participants prior to the in-person screening. The in-person screening will include a questionnaire to collect demographic information, medications and medical and reproductive history. A physical exam and ECG for screening purposes will also take place at this time.

The baseline visit will include neuropsychiatric and physical examinations and laboratory tests. Though eligibility will be assessed at baseline, participation may be terminated if the subject stops meeting entry criteria. Dementia is an exclusion criterion. We will screen for possible incipient dementia and mild cognitive impairment of the amnestic subtype. This will include reviewing an extensive history and mental status exam together with corroborating information with regard to functional skills. A MMSE score of \leq 23 or an established dementia diagnosis will mandate exclusion. The evaluation for dementia includes: 1) an interview by a trained study staff to identify physical and cognitive limitations; 2) a standard battery of hematologic studies; 3) neuropsychological examination (detailed below); and 4) psychiatric evaluation as detailed above. Adjudication of dementia is based on DSM-5 criteria (Knopman et al., 2001; Lyketsos et al., 2002).

Inclusion criteria are:

1) Current subjective memory complaints:

- Frequency of at least once per week
- Able to provide an example of a recent memory difficulty
- Self-reported decline in memory ability since 5-10 years ago
- Self-reported concern about memory problems

2) High cardiovascular risk defined as at least one of the following:

- 7.5 percentile risk or higher using ASCVD risk calculator
- Myocardial Infarction more than 6 months ago
- Diabetes
- Taking medication for blood pressure
- \geq 140/90 blood pressure
- Taking medication for lyperlipidemia
- LDL≥160

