3) Sufficient English proficiency and the 8th grade or higher reading level as determined by the word reading subtest of the Wide Range Achievement Test-IV (this criterion is necessary in order to ensure ability to participate in MET, which involves reading and writing and has a Flesch-Kinkaid school equivalency of 7th grade)
 4) Capacity to provide informed consent

Exclusion criteria are:

- 1) History of psychosis, bipolar disorder, alcohol/ drug dependence, or neurological disorder
- 2) Clinically significant depressive symptoms as indicated by a BDI score >17
- 3) Recent (within three months) surgery, anticipated surgery within next year, or unstable medical condition
- 4) Any disability preventing participation in MET or KK+KY (e.g., severe visual or hearing impairment)
- 5) Insufficient English proficiency to participate in either MET or KK+KY
- 6) Diagnosis of dementia
- 7) Mini Mental Health Examination score of 23 or below
- 8) Currently taking any psychoactive medication (stable on antidepressant and not currently depressed is OK)
- 9) Participation in a psychotherapy that involves cognitive training
- 10) Current yoga practice (frequency of once/week or greater)
- 11) Myocardial Infarction within the past 6 months

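### The step that combines imaging predictors selects them on remission, relapse or cognitive decline, none of which is defined, and remission does not fit the women enrolled

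*Combined protocol and SAP*

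**What the plan says.** The section Integration with Mood and Neurocognitive Measures sets out two stages.

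- **Stage one** relates imaging to change in mood and cognition. Summary scores are derived for mood, memory and executive functioning, and "Percent change in the mean Z scores will be calculated for each domain score and entered into analysis". A separate general linear model is fitted for each MRI method.
- **Stage two**, Integration of Predictive Variables, follows once the predictive validity of each measure has been examined. Of the MRI measures, "those that significantly predict remission/relapse or cognitive decline at follow-up will be combined for regression analysis", with the best single predictor taken from each modality. Then "The final analysis will include a step-wise multiple regression analysis of clinical outcomes".

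The Exclusion criteria remove women with "Clinically significant depressive symptoms as indicated by a BDI score >17" (item 2) and women with a "Diagnosis of dementia" (item 6), as well as those with a history of psychosis or bipolar disorder (item 1). Item 8 excludes current psychoactive medication but adds that "stable on antidepressant and not currently depressed is OK". Screening Procedures says otherwise: "Only participants currently not taking psychotropic medications prior to the initiation of the study will be enrolled". Screening for MCI allows women with mild cognitive impairment and plans to compare them with those who have subjective complaints only.

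The aims and hypotheses do not mention remission or relapse. Hypothesis 1 states: "Improved memory performance will be observed in women receiving KK+KY and MET at 12 weeks compared to baseline".

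**The concern.** The quoted sentence decides which MRI measures reach the combined model, so its outcome has to exist in this population and be stated well enough to compute. Remission fails the first test. Relapse and cognitive decline fail the second. The final regression does not settle the matter, because its clinical outcomes are unnamed.

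What is at stake is the pre-specification of the last imaging analysis. An analyst would have to pick the instrument, the cut-off and the visit, possibly after seeing which choice lets measures through. The outcome would also differ from the one in stage one, so a measure that tracks memory gain in its own model could be dropped at the gate for failing to predict something else.

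**Working it through.** **Can each outcome occur, and is it defined?**

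| Outcome | Who could have it | Definition in the protocol |
|---|---|---|
| Remission | No identifiable group: BDI above 17 and dementia are excluded at entry | None |
| Relapse | Women with treated, non-current depression, if admitted; item 8 and Screening Procedures conflict | None |
| Cognitive decline | Any woman, including those with MCI | None |

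Table 4 repeats the BDI and MMSE at weeks 12, 24 and 48, so instruments exist from which relapse or decline could be built, but no rule is given. The Clinical Dementia Rating is at screening only. The word follow-up does not fix a visit either: the abstract and the study design use it for 6 and 12 months, while Study intervention procedures also applies it to the 12-week assessment.

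**How far does the number of decliners depend on the missing definition?** The documents give no decline rate. A rough range comes from the pilot memory means and SDs in Table 2, assuming normality and a retest correlation ρ of 0.5 to 0.8. The SD of change is √(s₀² + s₁² − 2ρs₀s₁).

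- HVLT delayed recall, yoga arm, week 12, ρ = 0.5: mean change 9.48 − 9.03 = 0.45; SD of change √(2.70² + 1.86² − 2×0.5×2.70×1.86) = 2.39. P(any drop) = Φ(−0.45/2.39) = 0.43. P(drop of at least 1 baseline SD) = Φ((−2.70 − 0.45)/2.39) = 0.09.
- WMS immediate recall, MET arm, week 24, ρ = 0.8: mean change 24.72 − 18.27 = 6.45; SD of change 4.79. P(any drop) = Φ(−6.45/4.79) = 0.09. P(drop of at least 1 SD) = Φ((−7.90 − 6.45)/4.79) = 0.001.

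Over the memory rows checked (HVLT total and delayed, WMS immediate and delayed, Rey-Osterreith 3-minute), any drop ranges from 9% to 43% and a 1 SD drop from 0.1% to 12%. The Recruitment section expects 35–36 completers per group at 12 months, or 70–72 women. That gives about 6–31 decliners under the first rule and 0–9 under the second. The pilot enrolled both sexes with MCI, so these rates may not carry over.

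**Illustration: the cost if decline were coded yes/no.** The plan states no power for this step, so there is no figure to reproduce. Inputs: n = 71 (middle of 70–72, assuming every completer has usable scans); two-sided α = 0.05 (Data analysis); true correlation r = 0.30 between an imaging measure and cognitive change (assumed).

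- Power ≈ Φ(atanh(r)·√(n − 3) − 1.96).
- Splitting a normal score so that a fraction p are decliners multiplies r by φ(z_p)/√(p(1 − p)).

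| Outcome | Factor | r after split | Power, n = 71 |
|---|---|---|---|
| Continuous change | 1 | 0.300 | Φ(0.3095×8.246 − 1.96) = 72% |
| 5% decliners | 0.473 | 0.142 | 22% |
| 12% decliners | 0.616 | 0.185 | 34% |
| 30% decliners | 0.759 | 0.228 | 48% |
| Even split | 0.798 | 0.239 | 52% |

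Under this model no cut-off matches the continuous score.

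**Does stage one already supply a usable outcome?** In substance yes, but not in percent form. Data analysis standardises each test to mean 0 across all participants. Percent change divides by a baseline score that lies near zero for many women, where it becomes very large, and is negative for many others, where it reverses sign. Absolute change has neither problem.

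**The case against.** The best defence is that this is loose wording in a late exploratory step. Stage one already relates each MRI method to continuous change in mood, memory and executive function, so the question of which imaging measures accompany a better response is addressed. That is correct. A reader who infers that the trial cannot answer that question goes further than the documents allow.

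Three other inferences also go too far.

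- **That relapse is impossible, or the whole outcome void.** Item 8 allows women who are stable on an antidepressant and not depressed; they could relapse, and the BDI is repeated. Women with MCI are admitted and could decline. Only remission lacks a population.
- **That few women will decline.** Hypothesis 1 predicts a mean improvement at 12 weeks. It gives no individual decline rate and says nothing about 6 or 12 months. The pilot-based range shows that the count turns on the rule chosen.
- **That the plan dichotomises decline and so halves its power.** No cut-off or logistic model is stated, and regression is compatible with a continuous score. Using the 90 completers expected at 12 weeks, the same formula gives 82% for a continuous score against 41% with 12% decliners. Those figures still depend on a yes/no coding that the plan does not contain, and 90 is not the number expected at 12 months.

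What remains is that the gate names one outcome without a population and two without definitions, and that it departs from the outcome used in the preceding stage.

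**Conclusion.** The concern holds for the predictor-integration step. That remission does not fit the eligible women follows from the exclusion criteria and needs no assumption. That remission, relapse and cognitive decline all lack a definition, instrument, threshold and visit is a matter of reading the text.

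The power figures (about 72% against 34% or 52%) only show why a continuous outcome is preferable should decline be coded yes/no. They rest on an assumed correlation of 0.30, an assumed decline rate, normality and about 71 women with usable scans.

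The stage-one imaging models, the primary memory comparison and the executive-function comparison do not depend on this sentence, and their stated power is untouched. The point is limited in scope but worth correcting, because the step cannot be carried out as pre-specified.

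**What to change.** Under Integration of Predictive Variables, replace remission, relapse and cognitive decline as the selection outcome with absolute change from baseline in the memory, executive and mood domain scores at 6 and 12 months. Name the same outcomes for the final regression, and change percent to absolute in stage one so that the two stages agree. List the measures that make up the mood score, since the section does not.

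Add week 12 only once the schedule is reconciled. The primary outcome definition, and the statement under Measures and Outcomes that all outcomes are taken at week 12, require cognitive testing then. The Neuropsychological tests paragraph and Table 4 show the battery at baseline and at 6 and 12 months only.

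If relapse or decline is kept as a supplementary outcome, state its instrument, threshold and visit. The two statements on psychotropic medication at entry must also be reconciled, because they determine whether anyone is at risk of relapse.

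The cost is analysis-plan wording. The 6- and 12-month cognitive battery and the mood scales are already scheduled, so no new data are needed for those visits.
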